### **13.4 Discontinuation of the study**

Novartis reserves the right to discontinue this study under the conditions specified in the clinical study agreement. Specific conditions for terminating the study are outlined in [Section 9.1.4](#).

### **13.5 Publication of study protocol and results**

The protocol will be registered in a publicly accessible database such as clinicaltrials.gov. In addition, after study completion (defined as last patient last visit) and finalization of the study report the results of this trial will be submitted for publication and posted in a publicly accessible database of clinical trial results, such as the Novartis clinical trial results website and all required Health Authority websites (e.g. clinicaltrials.gov, FDA etc.).

For details on the Novartis publication policy including authorship criteria, please refer to the Novartis publication policy training materials that were provided to you at the trial investigator meetings.

### **13.6 Study documentation, record keeping and retention of documents**

Each participating site will maintain appropriate medical and research records for this trial, in compliance with Section 4.9 of the ICH E6 GCP, and regulatory and institutional requirements for the protection of confidentiality of patients. As part of participating in a Novartis-sponsored study, each site will permit authorized representatives of the Sponsor(s) and regulatory agencies to examine (and when required by applicable law, to copy) clinical records for the purposes of quality assurance reviews, audits and evaluation of the study safety and progress.

Source data are all information, original records of clinical findings, observations, or other activities in a clinical trial necessary for the reconstruction and evaluation of the trial. Examples of these original documents and data records include, but are not limited to, hospital records, clinical and office charts, laboratory notes, memoranda, patients' diaries or evaluation checklists, pharmacy dispensing records, recorded data from automated instruments, copies or transcriptions certified after verification as being accurate and complete, microfiches, photographic negatives, microfilm or magnetic media, x-rays, and patient files and records kept at the pharmacy, at the laboratories, and medico-technical departments involved in the clinical trial.

Data collection is the responsibility of the clinical trial staff at the site under the supervision of the site Principal Investigator. The study electronic case report form (eCRF) is the primary data collection instrument for the study. The investigator must ensure the accuracy, completeness, legibility, and timeliness of the data reported in the eCRFs and all other required reports. Data reported on the eCRF, that are derived from source documents, must be consistent with the source documents or the discrepancies must be explained. All data requested on the eCRF must be recorded. Any missing data must be explained. For electronic CRFs an audit trail will be maintained by the system.

The investigator/institution must maintain the trial documents as specified in Essential Documents for the Conduct of a Clinical Trial (ICH E6 Section 8) and as required by applicable regulations and/or guidelines. The investigator/institution must take measures to prevent accidental or premature destruction of these documents.

Essential documents (written and electronic) must be retained for a period of not less than fifteen (15) years from the completion of the Clinical Trial unless Sponsor provides written permission to dispose of them or, requires their retention for an additional period of time because of applicable laws, regulations and/or guidelines.

### **13.7 Confidentiality of study documents and patient records**

The investigator must ensure anonymity of the patients; patients must not be identified by names in any documents submitted to Novartis. Signed informed consent forms and patient enrollment log must be kept strictly confidential to enable patient identification at the site.

### **13.8 Audits and inspections**

Source data/documents must be available to inspections by Novartis or designee or Health Authorities.

Novartis maintains a robust Quality Management System (QMS) that includes all activities involved in quality assurance and quality control, to ensure compliance with written Standard Operating Procedures as well as applicable global/local GCP regulations and ICH Guidelines.

Audits of investigator sites, vendors, and Novartis systems are performed by auditors, independent from those involved in conducting, monitoring or performing quality control of the clinical trial. The clinical audit process uses a knowledge/risk based approach.

Audits are conducted to assess GCP compliance with global and local regulatory requirements, protocols and internal SOPs, and are performed according to written Novartis processes.

### **13.9 Financial disclosures**

Financial disclosures must be provided by study personnel who are directly involved in the treatment or evaluation of patients at the site - prior to study start.

## **14 Protocol adherence**

This protocol defines the study objectives, the study procedures and the data to be collected on study participants. Additional assessments required to ensure safety of participants should be administered as deemed necessary on a case by case basis. Under no circumstances including incidental collection is an investigator allowed to collect additional data or conduct any additional procedures for any purpose involving any investigational drugs under the protocol, other than the purpose of the study. If despite this interdiction prohibition, data, information, observation would be incidentally collected, the investigator shall immediately disclose it to Novartis and not use it for any purpose other than the study, except for the appropriate monitoring on study participants.

Investigators ascertain they will apply due diligence to avoid protocol deviations. If an investigator feels a protocol deviation would improve the conduct of the study this must be considered a protocol amendment, and unless such an amendment is agreed upon by Novartis and approved by the IRB/IEC and Health Authorities, where required, it cannot be implemented. All significant protocol deviations will be recorded and reported in the CSR.

### **14.1 Amendments to the protocol**

Any change or addition to the protocol can only be made in a written protocol amendment that must be approved by Novartis, health authorities where required, and the IRB/IEC prior to implementation.

Only amendments that are required for participant safety may be implemented immediately provided the health authorities are subsequently notified by protocol amendment and the reviewing IRB/IEC is notified.

Notwithstanding the need for approval of formal protocol amendments, the investigator is expected to take any immediate action required for the safety of any participant included in this study, even if this action represents a deviation from the protocol. In such cases, Novartis should be notified of this action and the IRB/IEC at the study site should be informed according to local regulations.

## 16 Appendices

MBG453, as a mAB, is not expected to have many interactions, unlike small molecules that are metabolized by the CYP450 enzymes and may induce or inhibit some of these enzymes or other transporters. Therefore, there is no long list of prohibited meds that need to be listed in an appendix. Please refer to [section 6.2.2](#).

### 16.1 Appendix 1: Clinically notable laboratory values and vital signs

There are no specific notable range criteria for this study; however, the local and central laboratory will flag laboratory values falling outside of the normal range, on the local and central laboratory report (as applicable) (which the investigator should sign off) as per local practice, and the investigator will report any values considered clinically significant in the eCRF. The investigator will also report any vital signs, local ECG values considered clinically significant in the eCRF.

## 16.2 Appendix 2: Liver event and laboratory trigger definitions & follow-up requirements

**Table 16-1 Liver event and laboratory trigger definitions**

	Definition/ threshold
LIVER LABORATORY TRIGGERS	3 x ULN <ALT / AST $\leq$ 5 x ULN 1.5 x ULN <TBL $\leq$ 2 x ULN
LIVER EVENTS	ALT or AST $>5 \times$ ULN
	ALP $>2 \times$ ULN (in the absence of known bone pathology)
	TBL $>2 \times$ ULN (in the absence of known Gilbert syndrome)
	ALT or AST $>3 \times$ ULN and INR $>1.5$
	Potential Hy's Law cases (defined as ALT or AST $>3 \times$ ULN and TBL $>2 \times$ ULN [mainly conjugated fraction] without notable increase in ALP to $>2 \times$ ULN)
	Any clinical event of jaundice (or equivalent term)
	ALT or AST $>3 \times$ ULN accompanied by (general) malaise, fatigue, abdominal pain, nausea, or vomiting, or rash with eosinophilia
	Any adverse event potentially indicative of a liver toxicity*

\*These events cover the following: Hepatic failure, fibrosis and cirrhosis, and other liver damage- related conditions; the non-infectious hepatitis; the benign, malignant and unspecified liver neoplasms TBL: total bilirubin; ULN: upper limit of normal

**Table 16-2 Follow up requirements for liver laboratory triggers with liver symptoms**

Criteria	Actions required	Follow-up monitoring
Potential Hy's Law case a	Discontinue the study treatment immediately Hospitalize, if clinically appropriate Establish causality Record the AE and contributing factors (e.g. conmeds, med hx, lab) in the appropriate CRF	ALT, AST, TBL, Alb, PT/INR, ALP and GGT until resolution c (frequency at investigator discretion)

Criteria	Actions required	Follow-up monitoring
ALT or AST		
>8 × ULN	
Discontinue the study treatment immediately
 
Hospitalize if clinically appropriate
 
Establish causality
 
Record the AE and contributing factors (e.g. comeds, med hx, lab) in the appropriate CRF
	ALT, AST, TBL, Alb, PT/INR, ALP and GGT until resolution c (frequency at investigator discretion)
>3 × ULN and INR >1.5	
Discontinue the study treatment immediately
 
Hospitalize, if clinically appropriate
 
Establish causality
 
Record the AE and contributing factors (e.g. comeds, med hx, lab) in the appropriate CRF
	ALT, AST, TBL, Alb, PT/INR, ALP and GGT until resolution c (frequency at investigator discretion)
>5 to ≤8 × ULN	
Repeat LFT within 48 hours
 
If elevation persists, continue follow-up monitoring
 
If elevation persists for more than 2 weeks, discontinue the study drug
 
Establish causality
 
Record the AE and contributing factors (e.g. comeds, med hx, lab) in the appropriate CRF
	ALT, AST, TBL, Alb, PT/INR, ALP and GGT until resolution c (frequency at investigator discretion)
>3 × ULN accompanied by symptoms b	
Discontinue the study treatment immediately
 
Hospitalize if clinically appropriate
 
Establish causality
 
Record the AE and contributing factors (e.g. comeds, med hx, lab) in the appropriate CRF
	ALT, AST, TBL, Alb, PT/INR, ALP and GGT until resolution c (frequency at investigator discretion)

>3 to $\leq$ 5 $\times$ ULN (patient is asymptomatic)	Repeat LFT within the next week  If elevation is confirmed, initiate close observation of the patient	Investigator discretion  Monitor LFT within 1 to 4 weeks
---	---	--

Criteria	Actions required	Follow-up monitoring
ALP (isolated)		
>2 $\times$ ULN (in the absence of known bone pathology)	Repeat LFT within 48 hours  If elevation persists, establish causality  Record the AE and contributing factors (e.g. conmeds, med hx, lab) in the appropriate CRF	Investigator discretion  Monitor LFT within 1 to 4 weeks or at next visit
TBL (isolated)		
>2 $\times$ ULN (in the absence of known Gilbert syndrome)	Repeat LFT within 48 hours  If elevation persists, discontinue the study drug immediately  Hospitalize if clinically appropriate  Establish causality  Record the AE and contributing factors (e.g. conmeds, med hx, lab) in the appropriate CRF	ALT, AST, TBL, Alb, PT/INR, ALP and GGT until resolution c (frequency at investigator discretion)  Test for hemolysis (e.g. reticulocytes, haptoglobin, unconjugated [indirect] bilirubin)
>1.5 to $\leq$ 2 $\times$ ULN (patient is asymptomatic)	Repeat LFT within the next week  If elevation is confirmed, initiate close observation of the patient	Investigator discretion  Monitor LFT within 1 to 4 weeks or at next visit
Jaundice	Discontinue the study treatment immediately  Hospitalize the patient  Establish causality  Record the AE and contributing factors (e.g. conmeds, med hx, lab) in the appropriate CRF	ALT, AST, TBL, Alb, PT/INR, ALP and GGT until resolution c (frequency at investigator discretion)
Any AE potentially indicative of a liver toxicity*	Consider study treatment interruption or discontinuation	Investigator discretion

	Hospitalization if clinically	
--	-------------------------------	--

Criteria	Actions required	Follow-up monitoring
a Elevated ALT/AST >3 × ULN and TBL >2 × ULN but without notable increase in ALP to >2 × ULN		
b (General) malaise, fatigue, abdominal pain, nausea, or vomiting, or rash with eosinophilia		c Resolution is defined as an outcome of one of the following: (1) return to baseline values, (2) stable values at three subsequent monitoring visits at least 2 weeks apart, (3) remain at elevated level after a maximum of 6 months, (4) liver transplantation, and (5) death.

Based on investigator's discretion investigation(s) for contributing factors for the liver event can include: Serology tests, imaging and pathology assessments, hepatologist's consultancy; obtaining more detailed history of symptoms and prior or concurrent diseases, history of concomitant drug use, exclusion of underlying liver disease.

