**Table 6-4 Follow-up of abnormal liver chemistry results**

ALT	TBL	Liver Symptoms	Action
ALT increase without bilirubin increase:			
If normal at baseline: ALT $>3$ x	Normal		- No change to study treatment - Measure ALT, AST, ALP, GGT, TBL, INR, albumin and CK in 48- 72 hours (GLDH is recommended as well) - Follow-up for symptoms
If elevated at baseline: ALT $>2$ x baseline or $>200$ U/L (whichever occurs first)	For participants with Gilbert's syndrome: No change in baseline TBL	None	
If normal at baseline: ALT $>5$ x ULN for more than two weeks	Normal For participants with	None	- Interrupt investigational drug

If elevated at baseline: ALT >3 x baseline or >300 U/L (whichever occurs first) for more than two weeks	Gilbert's syndrome: No change in baseline TBL		
 
- Measure ALT, AST, ALP, GGT, TBL, INR, albumin and CK in 48- 72 hours (GLDH is recommended as well).
 
- Follow-up for symptoms.
 
- Initiate close monitoring and workup for competing etiologies.
 
- Investigational drug can be restarted only if another etiology is identified and liver enzymes return to baseline.
 

If normal at baseline: ALT >8 x	Normal	None	
ALT increase with bilirubin increase:			
If normal at baseline: ALT >3 x	TBL >2 x ULN (or INR >1.5)  For participants with Gilbert's syndrome: Doubling of direct bilirubin	None	
If elevated at baseline: ALT >2 x baseline or >200 U/L (whichever occurs first)			
If normal at baseline: ALT >3 x ULN	Normal or elevated	Severe fatigue, nausea, vomiting, right upper quadrant pain	
If elevated at baseline: ALT >2 x baseline or >200 U/L (whichever occurs first)			

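### Footnote a of Table 16-2 drops the conjugated-bilirubin condition from the Hy's Law definition and, read literally, stops both drugs for a narrow group of Gilbert participants

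*Protocol*

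**What the plan says.** **Two definitions.** Table 16-1 (Protocol, Appendix 2) defines a potential Hy's Law case by ALT or AST >3 x ULN and TBL >2 x ULN, and qualifies the bilirubin: "ULN [mainly conjugated fraction] without notable increase in ALP to" above 2 x ULN. Footnote a of Table 16-2 restates the three thresholds without that qualifier: "Elevated ALT/AST >3 × ULN and TBL >2 × ULN but without notable increase in ALP to >2 × ULN".

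**The action.** The row that footnote a defines says "Discontinue the study treatment immediately". Section 6.1 defines study treatment as sabatolimab plus the HMA, so the stop covers both.

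**How the protocol treats Gilbert bilirubin elsewhere.**
- Inclusion criterion 7 waives the 2 x ULN bilirubin limit for isolated Gilbert syndrome.
- The stand-alone TBL >2 x ULN entries in Tables 16-1 and 16-2 apply only "in the absence of known Gilbert syndrome".
- Table 6-4 (Section 6.5.1.1) counts a Gilbert participant as having no bilirubin increase under this condition: "For participants with Gilbert's syndrome: No change in baseline TBL". For such a participant without symptoms, and with ALT above 3 times the limit from a normal baseline, the action begins "No change to study treatment".

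**The competing row.** Table 16-2 also has a row for asymptomatic ALT or AST >3 to <=5 x ULN: repeat the liver tests, then "If elevation is confirmed, initiate close observation of the patient".

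**Precedence.** Section 6.5.1 sends the reader to Appendix 2 in addition to its own tables. It does not say which prevails.

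**The concern.** The conjugated-fraction condition separates bilirubin that suggests liver injury from the benign unconjugated bilirubin of Gilbert syndrome. The protocol makes that separation in Table 16-1, in both stand-alone bilirubin entries and in Table 6-4. Only the footnote that triggers a permanent stop lacks it.

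At stake is the management of individual participants. A site following the footnote to the letter would withdraw sabatolimab and the HMA from someone whose bilirubin has not changed since entry, while another table in the same protocol says to carry on.

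**Working it through.** No figure in the plan is in question, so the check sets the rules side by side.

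**Inputs.** Footnote a and the Table 16-2 rows; the Table 16-1 definition; Table 6-4; inclusion criteria 6 (ALT and AST <=3 x ULN) and 7.

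**Step 1: the rules as conditions (multiples of ULN).**
- Footnote a: ALT or AST >3, TBL >2, ALP not >2.
- Table 16-1: the same, and bilirubin mainly conjugated.
- Table 6-4, Gilbert, normal baseline ALT: ALT >3 with unchanged TBL and no symptoms means no change. Interruption needs ALT >5 for more than two weeks, ALT >8, doubled direct bilirubin, INR >1.5, or symptoms.

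**Step 2: one worked participant (illustrative values).** Gilbert syndrome, normal baseline ALT, direct bilirubin 0.3 and indirect 2.1 times the total-bilirubin ULN, both stable. TBL = 0.3 + 2.1 = 2.4; direct fraction = 0.3/2.4 = 12.5%. ALP <=2, INR <=1.5, no symptoms, no jaundice, new ALT 3.5.

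| Rule | Result |
|---|---|
| Footnote a, literal | Met: stop both drugs at once |
| Table 16-1 with the asymptomatic row | Not met: repeat tests, observe |
| Table 6-4 | No change |

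**Step 3: where the two definitions differ.** I kept this participant type and varied ALT over 3.5, 5.0, 5.1, 8.0 and 9.0, TBL over 1.2, 1.8, 2.0, 2.1, 2.5 and 3.0, and ALP over 1.0, 2.0 and 2.5. That gives 5 x 6 x 3 = 90 combinations.
- ALT 3.5 or 5.0: stop versus observe when TBL >2 (3 values) and ALP <=2 (2 values), so 2 x 3 x 2 = 12 combinations.
- ALT 5.1 or 8.0: another 12, but only the timing differs (at once, or after an elevation lasting more than two weeks).
- ALT 9.0: none, because Table 16-2 stops treatment above 8 x ULN anyway.
- The other 90 - 24 = 66 agree, including every one with TBL <=2 or ALP >2.

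These count chosen values, not participants.

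**Step 4: baseline ALT.** I took 40 ALT values from 3.01 to 4.96 x ULN, with TBL 2.5, ALP 1.5 and INR 1.0. Footnote a is met at every one and Table 16-1 at none.
- Normal baseline (2 levels, 80 points): Table 6-4 gives no change at 80 of 80, at one week and at three.
- Elevated baseline (7 levels from 1.1 to 3 x ULN, 280 points): within two weeks Table 6-4 never interrupts, although at some points none of its rows is triggered. After more than two weeks it interrupts where ALT exceeds 3 x baseline, at 34 + 25 + 10 = 69 of 280 points (baselines 1.1, 1.25 and 1.5). The 69 is the same for any assumed ALT ULN from 30 to 60 U/L.

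**Step 5: with the qualifier restored.** Footnote a is then met at none of these points, and no table calls for discontinuation.

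**The case against.** The best defence is structural. Table 16-1 holds the definitions and Table 16-2 the actions, so footnote a can be read as shorthand for a term defined just before it. That reading removes the conflict, and many investigators would adopt it. But the footnote is a complete definition in its own right, it does not refer back, and no precedence is stated.

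The title of Table 16-2, "Follow up requirements for liver laboratory triggers with liver symptoms", might seem to exclude asymptomatic participants. It does not settle the matter: the table contains expressly asymptomatic rows, and the Hy's Law row has no symptom condition.

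One could add that Section 6.5 forbids deviating from mandatory discontinuations. That is unsettled: Section 6.5.1 calls Appendix 2 further guidance, while Table 16-2 labels its actions as required. The point does not depend on it.

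A reader might infer more than the documents support:
- *That Table 6-4 always leaves treatment unchanged here.* It does so unconditionally only with normal baseline ALT (Step 4).
- *That Gilbert participants in general are at risk of being stopped.* Those with TBL <=2 x ULN or ALP >2 x ULN do not meet footnote a. With INR >1.5, jaundice, or listed symptoms alongside ALT >3 x ULN, Table 16-2 stops treatment under either definition.
- *That liver injury could be missed.* The literal footnote is the broader rule and errs toward stopping.
- *That the discontinuation rule also needs a Gilbert criterion based on doubled direct bilirubin.* Table 6-4 already uses that criterion, as a trigger to interrupt the investigational drug. Moving it into the Hy's Law row would make it a discontinuation of both drugs, even at TBL <=2 x ULN, where neither definition now stops treatment on bilirubin. Nor does leaving it out open a gap: if direct bilirubin in Step 2 doubles to 0.6, TBL is 2.7 and the direct fraction 0.6/2.7 = 22.2%. Table 16-1 is still not met, but Table 6-4 interrupts.

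**Conclusion.** The point holds as a minor drafting inconsistency in a stopping rule. The footnote that triggers immediate discontinuation is broader than the definition it restates. For the participant described in Step 2, the literal result contradicts both Table 16-1 and Table 6-4.

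The number affected is small and may be zero. Recruitment was halted with 39 enrolled, and the documents give neither the frequency of Gilbert syndrome nor the rate of ALT >3 x ULN, so no count or percentage is claimed. No hypothesis test, sample size, planned Hy's Law count or programmed laboratory grade changes.

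The conclusion rests on a literal reading of footnote a. The comparison with Table 6-4 also rests on its layout. Cell borders are lost in the public text, and the first Gilbert line sits beside the elevated-baseline entry. In the next row the same text begins on the normal-baseline line, which supports one cell covering both. If that is wrong, the conflict inside Appendix 2 remains.

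**What to change.** Add the mainly-conjugated qualifier to TBL >2 x ULN in footnote a, or replace the footnote with a reference to the Table 16-1 definition. Leave the doubling of direct bilirubin in Table 6-4 as an interruption trigger.

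Recruitment ended on 30 September 2022 and the latest SAP entry is marked as after database lock, so rewording does little for this trial. The useful step now is to search the existing laboratory and disposition listings for anyone who met footnote a but not Table 16-1, and to report whether treatment was stopped for that reason. The corrected wording should go into any roll-over or later protocol that reuses Appendix 2.

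The cost is one footnote and a one-off listing check. Table 8-5 already collects direct, indirect and total bilirubin, ALT, AST, alkaline phosphatase and INR, so no new data are needed.
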